Form B: Medical IRB Research Description

1. **Background:** The Tanglewood Trail walking group is a community-initiated walking group, spontaneously established in summer 2016. Community members meet at the Housing Authority in Whitesburg, KY and walk the approximately 1 kilometer Tanglewood Trail connecting the Housing Authority to the Farmer's Market. Participation in the walking group is open to the public. Participants that walk to the Farmer's Market on Wednesday evenings receive a \$5 voucher to the Farmer's Market and a \$10 voucher on Saturdays during the season (June-October). Adults 18 years and older receive one voucher each time they walk. Currently, there is no evaluation of the walking group program beyond the community tracking the name, number of walkers, and the number of vouchers distributed to walkers on each Wednesday and Saturday. This program was initiated by community members and UK researchers were not involved with its creation or tracking any component of the program.

The current proposed study will target non-pregnant healthy, 18+ years old, community members who are willing and able to walk the Tanglewood Trail on Saturday mornings, June-August 2017. Community members will be randomized into a walking group and a farmers market group. Both groups will receive farmers market vouchers of equivalent value. One group will meet at the Housing Authority and walk to the farmers market to obtain their vouchers and the other group will obtain their farmers market voucher at the farmers market. Both groups are welcome to walk the Tanglewood Trail if they would like, however those that are randomized into the walking group are expected to walk. However, people are not forced to walk and have the option to refuse to walk. We hypothesize that adults who regularly attend the walking group and subsequently purchase fruits and vegetables at the Farmer's Market will experience an increase in physical activity, fruit and vegetable intake, and community engagement, and a decrease in anthropometrics and biomarkers associated with adulthood chronic disease (including cholesterol, hemoglobin A1c, blood pressure, carotenoid status, weight, and waist circumference) beyond that of the farmers market voucher group only.

2. **Objectives:**

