- a) To educate Tanglewood Trail program participants about the health benefits of consuming a variety of fruits and vegetables, being physically active, and dietary strategies that can help protect their health from environmental pollution.
- b) Assess self-reported behavior change, knowledge change, and change in physical measurements (see below), and level of physical activity.

3. **Study Design:** The sample population consists of a convenience sample that is participating in a prospective study. This study will focus on nonpregnant healthy adult (ages 18+) community members who walk the Tanglewood Trail on Saturdays, June-August 2017.

Any interested community members who are 18 years or older, nonpregnant and able to voluntarily give their consent are welcome to join the study. One hundred participants will be randomized into one of two groups – a walking group and a farmer's market group.

The fifty participants randomized into the walking group will meet at the Housing Authority at a designated time each Saturday. When they arrive, they will be signed in by a community leader and receive a farmer's market voucher (**see attached**) for \$10 along with education material (5 of the 13 Saturdays). They will walk as a group to the farmer's market and hand their voucher to the market manager, who will give them \$10 in tokens to purchase fruits and vegetables at the market. The voucher will have two sides: one side will ask participants what fruits and vegetables they ate the past week; the second side will ask participants to check off what fruits and vegetables they purchase at the market that day. They will turn this in as they leave the market. The fifty participants randomized into the farmer's market group will meet at the farmer's market and sign in with a UK employee. They will receive the same voucher and education materials and follow the same procedure as the walking group. Participants randomized into this group will be allowed to walk if they want; no one will be dissuaded from engaging in physical activity. However, in order to receive their voucher, it is not required for them to walk.

Three times per month participants will be presented with education material concerning phytonutrients, the importance of fruit and vegetable intake, and how these factors might protect them from environmental pollutants. The education materials will be in the form of a.) a handout based on the Transtheoretical Model

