Form B: Medical IRB Research Description

(see attached example) or b.) Plate it Up Kentucky Proud recipe samples and cards (see attached example). A Registered Dietitian will be available to answer nutrition-based health questions once per month.

No participants will receive medications – neither real nor placebo.

Data will be a time series collection of finger-stick total cholesterol, LDL, HDL, triglycerides, hemoglobin A1c (cardiocheck meter), height, weight, waist circumference, carotenoid status (carotenoid RS, which is a non-invasive instrument that is a reliable indicator of fruit and vegetable intake (see attached), and a survey (see attached). Measurements will be taken twice – baseline data will be collected in May 2017, with follow-up data collected in early September 2017.

Finger stick tests will be conducted by University of Kentucky employees who have completed all necessary biohazard training (see attached IBC approval and certificates of completion). Lysol wipes will be available to wipe down equipment as needed. Hand sanitizer will be provided to each researcher to use between glove changes. Gloves will be changed between each participant. Heat packets will be available for participants with cold hands to make the finger stick go faster and easier. Lancets will be used to take the finger stick and all materials will be disposed of in sharps containers. All sharps containers will remain sealed until the research team returns to the University of Kentucky that same day to dispose of the sharps containers.

4. **Study Population:** Based on walking group numbers from summer 2016 we anticipate a maximum enrollment of 100 participants (18+ years old, nonpregnant). Previous research in Letcher County suggests the majority of participants will be white, ages 18-65, both male and female, of moderate health status. A prerequisite for participating in this study is the ability to walk approximately 1 kilometer to the Farmer's Market, nonpregnant, pre-supposing a baseline health status. Any interested community members over the age of 18 and in moderate or good health will be included. Since our focus is on changes in rates of chronic disease in adulthood, children will be excluded from study participation (but may walk the trail with their parents). Institutionalized adults, pregnant adults adults with impaired consent capacity, and prisoners will be excluded. No one will be excluded based on sex/gender or racial/ethnic identity.

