5. **Subject Recruitment Methods and Privacy:** A community leader will build a facebook group in April 2017 to help recruit subjects. Interested participants will be invited to an opening baseline data collection event in May 2017. Interested participants will be told about the study and that their involvement is completely voluntary. We will obtain consent from those that are interested in participating in the study. We will then invite consented participants to fill out a survey and have the above measurements (see section 3) taken in return for a farmer's market t-shirt. Participants will be randomized into one of the two groups, walking group or farmers market only group, and informed of their group in May, during baseline measurements.

Privacy will be maintained through de-identification of all survey and measurement data. The surveys and measurement data sheets will contain a cover sheet that has a place to record the participant's name. The next page will be where the first question is listed and a space for the survey code to be recorded. Once the survey has been coded the cover sheet will be removed from the post-surveys and shredded. Participants will be asked to indicate which fruits and vegetables they purchased at the market on shopping card (see attached). The card will have a place for their name and they will give them to the community leader before leaving the market. The community leader will collect these weekly and give them to UK researcher bi-weekly. The shopping card data will be matched to participants' measurement data on an electronic datasheet. Once all of the data has been collected in September the electronic list of names will be replaced with a code to de-identify participants, the cover sheets of the surveys that contain participant names will be shredded and the surveys and shopping cards will be stored securely in a locked drawer in the PI's locked office. The electronic data that is generated will be stored on a password protected computer. Throughout the study, any study materials that contain participant names will be stored in a locked filing cabinet in the PI's locked office. In the event this data is published it will be done so by aggregating the data without identifying individuals.

Form B: Medical IRB Research Description

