18. **Subject Complaints:** Participants can voice their concerns to the PI, Co-PIs, program manager, or the Office of Research Integrity, which is listed on the consent form.
19. **Research Involving Non-English Speaking Subjects or Subjects from a Foreign Culture:** N/A
20. **HIV/AIDS Research:** N/A
21. **PI-Sponsored FDA-Regulated Research:** N/A

Tanglewood Trail Walking Program in Rural Kentucky 2020 - SAP

A dependent t-test will be used for the difference in survey questions (environmental pollution knowledge, fruit and vegetable intake, and physical activity) between before and after the Tanglewood trail walking program.

When the sample size is 50, a dependent t-test with a 5% two-sided significance level will have 80% power to detect an effect size of 0.4 calculated from previous data.

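### Returning 2016 walkers and newcomers may be mixed in unknown proportion; recording and stratifying on prior participation is a cheap improvement

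*Combined protocol and SAP*

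**What the plan says.** Four features of the plan bear on this point.

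- **Source of the sample.** Section 4 (Study Population): "Based on walking group numbers from summer 2016 we anticipate a maximum enrollment of 100 participants". Section 2, objective (a), is aimed at participants in the existing programme. Section 3 (Study Design) opens entry more widely: "Any interested community members who are 18 years or older, nonpregnant and able to voluntarily give their consent are welcome to join the study". Section 5 names a Facebook group, to be built in April 2017, as a recruitment aid. The share of 2016 walkers expected is not given.
- **Description of the population.** Section 3: "This study will focus on nonpregnant healthy adult (ages 18+) community members who walk the Tanglewood Trail on Saturdays, June-August 2017". Section 1 instead describes people prepared and able to do the Saturday walk, and section 4 requires the ability to walk about 1 kilometre.
- **Allocation.** Section 5: "Participants will be randomized into one of the two groups", with no stratification factor named. Section 3 gives 50 per group. Section 1 says "those that are randomized into the walking group are expected to walk". The market group may walk if it wishes and gets its voucher either way (sections 1, 3 and 6). Section 9 says that the groups differ only in where they sign in.
- **Analysis.** The SAP plans a before-after paired t-test on survey items, with no covariate, subgroup or between-arm comparison.

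Section 1 also says that the community already records walkers by name.

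**The concern.** The hypothesis in section 1 is that the walking group gains more than the voucher-only group. Someone who spent the 2016 season walking the trail for vouchers may respond differently to a second season than a newcomer would, and may be more inclined to walk even if assigned to the market group. If so, prior participation predicts both the outcome and the amount of crossover. It could be known at baseline from one question, and the community log offers a check on the answer.

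The plan uses it nowhere. Two things follow. The groups may differ by chance in their share of returners, and the planned analysis would not adjust for it. And if the groups turn out alike, the visible plan offers no way to ask whether returners had already changed or had walked in both groups. Stratification cannot be added once people are allocated. Linkage to the community log ends when the list of names and codes is deleted after post-survey entry (sections 6, 10 and 13; section 14 gives January 2020 as the latest date).

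Separately, the section 3 focus sentence defines the whole population by walking during the study months, which does not fit a comparator that need not walk.

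**Working it through.** **1. The plan's own figure.** The SAP says that with 50 people "a dependent t-test with a 5% two-sided significance level will have 80% power to detect an effect size of 0.4". Normal approximation: n = ((1.960 + 0.842)/0.4)² = 49.06, rounded up to 50; power at n = 50 is 80.7%. The exact paired t (49 degrees of freedom) gives 79.2%. The figure reproduces, but it concerns change within one set of 50 people, not a difference between groups.

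**2. Chance imbalance.** Inputs: 100 people and 50 per group (section 3). The share of returners is an assumption, taken as 25%, 50% or 75%.

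With K returners among 100, the number X in one group is hypergeometric. For K = 50:

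- Var(X) = 50 × 0.5 × 0.5 × (50/99) = 6.31, so SD(X) = 2.51.
- The arm difference in share is (2X − 50)/50, with SD 2 × 2.51/50 = 0.100, or about 10 percentage points. The 95% range is about ±20 points.
- The probability of a gap of 20 points or more (10 people) is 7.1%.

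For K = 25 or 75 the SD is 8.7 points, and the probability of a gap of at least 20 points is 2.0%.

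**3. What an imbalance could do.** If returners and newcomers differ in mean change by δ standard deviations (assumed), a 20-point gap shifts the arm difference by 0.20 × δ. That is 0.04, 0.08 or 0.16 SD for δ = 0.2, 0.4 or 0.8. The standard error of a between-arm difference with 50 per group is √(2/50) = 0.20 SD. Even an unlucky split therefore moves the estimate by less than one standard error in this range. That is worth preventing when prevention is cheap, but it is not a fatal flaw.

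**4. Crossover walking, which is a different mechanism.** Let f be the fraction of the between-arm effect lost, for example because market-group members walk. The documents do not give f. Treating 0.4 as the undiluted between-arm effect (an assumption, since the SAP's 0.4 is a within-person change), the exact two-sample t with 50 per group gives:

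| f | effect | power |
|---|---|---|
| 0 | 0.4 | 50.8% |
| 0.25 | 0.3 | 31.8% |
| 0.50 | 0.2 | 16.8% |
| 0.75 | 0.1 | 7.9% |

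This loss comes from walking that the protocol allows. It would be the same whether or not allocation was stratified. It shows why one would want to be able to examine a null result.

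**5. Size of the strata.** If half were returners, each stratum would hold about 25 per group. The effect detectable with 80% power is (1.960 + 0.842) × √(2/25) = 0.79, about 0.8 SD. Results by stratum can only be descriptive.

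**The case against.** A reader might infer more than the documents support, in four ways.

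- **That the trial recruits 2016 walkers.** The section 3 sentence concerns walking in June-August 2017, the study period. Entry is open to any interested adult, and section 4 uses the 2016 numbers only to project a maximum.
- **That returners have little room to change.** The programme season is June-October (section 1) and baseline is in May (section 3), before the season starts. No baseline data or evidence of a lasting 2016 effect is given.
- **That returners in the market group will probably keep walking.** They may. But vouchers in the existing programme went to those who walked, and the market group's voucher does not depend on walking, so that incentive has gone.
- **That ignoring prior participation at randomisation weakens the contrast.** It does not. Simple randomisation is unbiased, and a valid between-arm test already allows for chance imbalance. Dilution would come from permitted walking, which stratifying leaves in place.

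All four corrections stand. It can also be said that the factor is unquantified, that the survey covers physical activity (section 13) and, since its attachment is not shown, may already ask about 2016, and that the SAP's lack of any between-arm test is the more basic gap. These are fair. They limit the weight of the point but do not remove it: no visible text uses prior participation in allocation or analysis, and the opportunity to stratify passes once people are allocated.

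**Conclusion.** The point holds as a low-cost improvement, not as a source of bias. The sample may mix returners and newcomers in a proportion that the documents do not state. Prior participation is a plausible, though unproven, predictor of response and of walking in the market group, and the plan does not use it.

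The allocation risk is modest. If half of the 100 were returners, the SD of the arm difference in their share is about 10 points, with about a 7% chance of a gap of 20 points or more; at a quarter or three quarters it is 8.7 points and about 2%. The larger practical loss is interpretive: on the visible text, a null result could not be examined for carry-over or crossover walking.

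These figures rest on 50 per group being enrolled and on the assumed share of returners. The documents do not support a claim that the contrast is weakened by the way people are randomised.

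**What to change.** 1. Ask one question at the May baseline: did the person walk with the group in 2016? Use the answer to assign the stratum, because section 5 has people told their group at the same event. Check it against the community's name log before the name-code list is deleted. The researchers were not involved in that log (section 1), so the community's agreement is needed.
2. Randomise within returning and new strata from two blocked lists.
3. Add to the SAP the between-arm comparison that section 1's hypothesis requires, with the stratum as a covariate. Show results by stratum descriptively, without subgroup tests.
4. Reword the section 3 focus sentence to agree with section 1, so that the population is defined by readiness and ability to walk and not by walking during the study.

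This balances prior participation and makes its influence visible. It does not reduce permitted walking in the market group; measuring that would also need a record of actual walking in both groups.

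Cost: one extra question, two lists instead of one at the baseline event, a check against the log, and one degree of freedom in the analysis. No extra participants or visits are needed.

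### The SAP's before-after t-test treats every participant's change as independent, although adults who live together may enrol and nothing in the plan identifies them

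*Combined protocol and SAP*

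**What the plan says.** Section 3 (Study Design) makes the individual the unit of allocation: "One hundred participants will be randomized into one of two groups". Section 5 repeats this for the May event: "Participants will be randomized into one of the two groups, walking group or farmers market only group". Neither section describes the allocation method.

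Entry is wide: "Any interested community members who are 18 years or older, nonpregnant and able to voluntarily give their consent are welcome to join the study". No section limits enrolment to one adult per household, and none says that shared residence is recorded. Section 1 shows that the existing programme gives vouchers per adult ("Adults 18 years and older receive one voucher each time they walk"), and Section 4 expects families on the trail ("children will be excluded from study participation (but may walk the trail with their parents"). Relatives enrolling together is therefore plausible, though no section reports that it happens.

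The SAP has one method, a dependent t-test of before-after change in three survey areas: pollution knowledge, fruit and vegetable intake, and physical activity. Its power statement takes a sample of 50, "a dependent t-test with a 5% two-sided significance level", 80% power and an effect size of 0.4. It has no household term and no robust variance. It does not say which 50 participants it means. The number equals the size of one arm in Section 3 ("The fifty participants randomized into the walking group will meet at the Housing Authority").

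**The concern.** A dependent t-test removes the correlation between the two measurements on one person. It does nothing about correlation between persons. Two adults who share a kitchen are likely to change their fruit and vegetable intake together, and may also walk together. If their changes are positively correlated, 50 change scores carry less information than 50 independent ones. The usual standard error is then too small, confidence intervals are too narrow, and the test rejects more often than its stated 5%.

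The information needed to correct this could also be lost. Sections 5, 9, 10, 13 and 14 provide for shredding the name sheets and deleting the list that links names to codes. Unless household is captured in coded form before then, a later correction or sensitivity analysis may be impossible.

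**Working it through.** **1. The SAP's own figure.** Inputs from the SAP: n = 50, effect size 0.4, two-sided 5%. Using the noncentral t distribution with 49 degrees of freedom and noncentrality 0.4 × √50 = 2.83, power is 79.2%. The normal approximation gives 80.7%. The stated 80% is reproduced. The exact n for at least 80% is 52. All of this assumes 50 independent change scores.

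**2. Assumptions.** The documents give neither of the two quantities needed, so both are assumed and shown as ranges:
- f, the share of participants who live with one other participant: 0.2 to 0.6
- r, the correlation of change scores within a household: 0.3 to 0.7

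**3. Both household members in the analysed sample.** The variance of the mean change is multiplied by D = 1 + f × r. The actual level of the uncorrected test is 2 × (1 − Φ(1.96/√D)).

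**4. The 50 are one arm after individual 1:1 allocation of 100.** A co-enrolled pair falls in the same arm with probability 49/99 = 49.5% and is split with probability 50/99 = 50.5%. Only same-arm pairs add correlation within that arm, so the expected factor is D = 1 + f × (49/99) × r.

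| f | r | D, both analysed | Actual level | D, one arm of 50 | Actual level |
|---|---|---|---|---|---|
| 0.2 | 0.3 | 1.06 | 5.7% | 1.03 | 5.3% |
| 0.3 | 0.5 | 1.15 | 6.8% | 1.07 | 5.9% |
| 0.6 | 0.7 | 1.42 | 10.0% | 1.21 | 7.5% |

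Example for the middle row: 1 + 0.3 × 0.5 = 1.15; 1.96/√1.15 = 1.828; 2 × (1 − Φ(1.828)) = 6.8%.

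**5. Effect on power.** With a correct standard error, 50 participants count as 50/D. For D = 1.06 this is 47.2 and power is 77%. For D = 1.42 it is 35.2 and power is 64%. In the one-arm case the range is 78% to 71%.

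**6. Does the same apply to a between-arm test?** Individual allocation was simulated with a two-sample t-test, 50 per arm, 40,000 runs for each combination of f = 0.4 or 1.0 with r = 0.3 or 0.5. Rejection under no effect was 4.9% to 5.2%. Household correlation alone does not inflate that test.

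**The case against.** **The premise is assumed.** No section reports a co-enrolled household, and f and r have no source in the documents. Section 13 says the survey asks about demographics. The survey itself is not shown and may already contain a household question. This stands. It makes the size uncertain, and at the low end the effect is small. It does not remove the gap, because neither the allocation nor the SAP uses household.

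**A reader might infer that splitting households contaminates the market arm through shared produce and handouts.** The documents do not support this. Section 1 gives both groups vouchers of equal value, Section 3 gives both the same vouchers and education, and Section 9 says the arms differ only in where people sign in. Sharing food or leaflets therefore carries nothing specific to one arm across to the other. Only walking could carry over, and the market arm may walk in any case: "Participants randomized into this group will be allowed to walk if they want". What remains is extra walking prompted by a relative in the other arm. That could dilute the contrast hypothesised in Section 1, but the documents give no basis for its size, and the SAP has no between-arm test on which it would act.

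**A reader might also infer that the 5% level fails for every analysis.** It does not. Step 6 shows no inflation for an individually randomised arm comparison. Nor does the point reach carotenoid status as planned, since the SAP tests survey outcomes only.

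**Allocating whole households would be the obvious cure.** It has a price. It would bring the full factor 1 + f × r into the arm comparison, up to 1.42 on the range above, so that 100 participants would count as about 100/1.42 = 70.

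**Conclusion.** The point holds for the before-after test. The plan admits co-resident adults without identifying them, and its only test assumes that their changes are independent. If 20-60% of participants are in two-adult households and their changes correlate at 0.3-0.7, the actual level is 5.7-10% with both members analysed, or about 5.3-7.5% if the 50 are one arm. If few co-resident adults enrol, or their changes are uncorrelated, there is little or no error.

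This is a modest, inexpensive improvement and not a flaw that invalidates the trial. It does not show general contamination between arms or a false significance level for an arm comparison.

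**What to change.** - **Sections 5 and 7 (May baseline event):** ask each person whether they live with another participant. Give adults of one household a common household code.
- **Sections 5, 10, 13 and 14 (records):** keep that code in the de-identified data set after the names and the linking list are deleted. It needs no name or address.
- **SAP:** keep the mean before-after change as the estimate, but compute its standard error, test and interval with a variance clustered on household. State which participants form the 50.

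The cost is one question and one line in the SAP. Intervals widen only if households co-enrol and their changes correlate: by √1.06 to √1.42, or about 3% to 19%, with both members analysed, and by about 1% to 10% for one arm. If no households co-enrol, the result is essentially the planned t-test.

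Allocating each household as a unit is optional. It would limit crossover in walking within households, but it costs precision in the arm comparison and could leave the arms a few people away from 50 each.
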